3.1. Study Design

This study will evaluate the effect of I-ACT with Check Yourself on adolescent-perceived quality of care (i.e., satisfaction and perception of PCP communication), motivation for health, and health risk behaviors using a stepped wedge study design. The study will take place in 6 participating PSPRN affiliated clinics, where the system of interventions (I-ACT with Check Yourself) will be rolled-out sequentially to the clinics, chosen in random order, over spaced time intervals (see Figure 1). We refer to pre-implementation of I-ACT with Check Yourself, as the control period and post-implementation as the intervention (i.e., case) period.

Figure 1: Stepped Wedge Study Design and Timeline

We anticipate that approximately 30% of youth approached will participate in the study. Thus, we will invite approximately 1000 adolescent/caregiver dyads to participate in the study, in order to yield 300 adolescent/caregiver dyad participants in our total sample. Upon enrollment, caregiver participants will be asked to complete a brief (10-minute) web-based questionnaire about their education/occupation, their adolescent's health history, and an open-ended question about what they would like to get from PCPs for themselves and their adolescent. Adolescents who enroll in the study will receive either electronic health screening alone (i.e., control group) if

their clinic appointment occurs in the pre-I-ACT implementation period or Check Yourself (i.e., intervention group) if their clinic appointment occurs in the post-implementation period.

At baseline (T1), adolescents will be asked to complete a web-based screening survey that includes questions about guideline-recommended health risk behavior screening areas, including substance use, nutrition, physical activity, sexual behavior, depressive symptoms, and safety. The screener questions themselves are current standard of care. Adolescents will also be asked to report their age, gender, race/ethnicity, interest in discussing health risks with the PCP, and self-efficacy.

Adolescents in the control group will complete the web-based screening survey for research purposes, but neither they nor their PCP will receive feedback about their health behaviors. PCPs will screen and counsel the patient as they would normally do under usual care conditions, consistent with the current standard of care.

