During the intervention period, participating PCPs will receive adolescent-centered communication training, based on the tenets of motivational interviewing, to reinforce healthy behavior choices and to engage youth and parents to reduce risk behaviors as appropriate. PCPs will also receive three feedback reports (baseline, 2 months and 4 months) on adolescent-reported receipt of counseling on each of the target behaviors and adolescent-reported visit satisfaction and follow-up care. PCPs will not be asked to complete any study questionnaires; all of the outcome data will be gathered directly from adolescents and caregivers. Outcome data for the three feedback reports will be given to providers in aggregate form and will be void of individual identifiers.

Adolescents in the intervention group will receive full personalized motivational feedback following completion of the screening survey, both with web-based delivery. Their PCPs will receive a summary report which will include specific information on the adolescent's responses that will allow them to reinforce healthy behavior choices and implement further brief, in-person interventions for moderate to high risk adolescents. The personalized feedback to the participant and provider is consistent with current standard of care. However, the electronic method of delivery is unique to this project.

In order to administer follow-up surveys, we will ask adolescents to provide an email address, cell phone number, or phone number. One day (T2) following their PCP appointment, adolescent participants will be asked via email, text message or phone to complete a survey about their motivation for health, perception of PCP communication, and experiences. Both adolescents and their caregivers will be asked about their satisfaction with treatment during the appointment with their PCP. In addition, caregivers will be asked open-ended questions to assess the provider's delivery of caregiver education regarding strategies to reduce health risks for their child during the visit.

Three (T3), six (T4) and twelve (T5) months following their PCP appointment, adolescent participants will be asked via email, text message or phone to complete all assessments

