administered at T1 and T2 except the questionnaires related to delivery of preventive counseling, demographics, interest in discussing health risks with PCP, and self-efficacy. Additionally, adolescents will be asked about follow-up care they may have received. At T2 and T3, adolescent participants will be asked about their general satisfaction with their provider and will be asked 3-4 follow-up questions to ascertain satisfaction with the Check Yourself app and study. These surveys are not standard of care, because they are not collected as part of an appointment; however, the probability and magnitude of discomfort associated with the completion of these surveys is no greater than ordinarily encountered in daily life or during the performance of routine psychological examinations/tests or medical care.

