3.2. Measures by Construct and Time point

Tables 1 and 2 describe the study measures by construct.

Table 1: Measures used in the study, organized by construct and method.

Measures and Constructs	Time point
Moderators	
Gender, age, race, household composition, school, truancy, support, goals, interest in discussing health risks with provider	T1(A)
Number of visits with provider	T2(A)
Health Self-Efficacy	T1(A), T2 (A), T3(A), T4(A), T5(A)
Caregiver Concerns	
Guidelines for Adolescent Preventative Services Caregiver Questionnaire: adolescent health risk behavior concerns.	T1(C)
Perception of provider engagement with the caregiver	T2 (C)
Intermediary Targets	
Health Motivation (Readiness to Change Rulers): Self-report used to assess adolescent motivation for change among specific health behaviors.	T1(A), T2 (A), T3(A), T4(A), T5(A)
Adolescent Report of the Visit: adolescent-report of the PCPs' delivery of risk behavior screening and counseling based on risk level.	T2 (A)
Interval Receipt of Care: adolescent self-report of extent of follow up care.	T3 (A), T4(A), T5(A)
Main Outcomes: Satisfaction & Perception of PCP Communication	

Satisfaction Questionnaire: self-report of satisfaction with care based on items adapted from the Consumer Assessment of Healthcare Providers and Systems (CAHPS) measure.	T2(A/C)
Adolescent Perception of Patient-Centeredness: adolescent self-report of how adolescents feel about visits with their primary caregiver.	T2(A)
Main Outcomes: Health Risk Dimensions*	
Alcohol Consumption and Marijuana Use: self-report based on items about typical quantity and frequency of drinking, smoking/using tobacco, and marijuana use (each calculated separately) over the past 30 days.	T1(A), T3(A), T4(A), T5(A)
Fruit and Vegetable Screener: self-report of fruit and vegetable consumption.	T1(A), T3(A), T4(A), T5(A)
Physical Activity Screener: self-report of physical activity.	T1(A), T3 (A), T4(A),T5(A)
Sexual Risk: self-report of sexual activity, birth control, and condom use.	T1(A), T3(A), T4(A), T5(A)
Patient Health Questionnaire-9 (PHQ-9): self-report of DSM-V symptoms for depression.	T1(A), T3(A), T4(A), T5(A)
Safety: self-report to assess behaviors that contribute to unintentional injuries (e.g., seat belt use, helmet use).	T1(A), T3(A), T4(A), T5(A)

Key: T1 = Timepoint 1 (Baseline) T4 = Timepoint 4 (6 month)
T2 = Timepoint 2 (1-day) T5 = Timepoint 5 (1 year)
T3 = Timepoint 3 (3-month)
A = Adolescent survey

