The goal of any heterogeneity of treatment effects analyses will be to ascertain whether treatment effects vary significantly across subgroups of patients and to identify subgroups of patients that achieve the greatest benefit from part or entire treatment regimen. (PCORI Methodology Standard HT-1) Based on our current knowledge, we hypothesize that treatment effects may vary substantially across age groups (13-15 yrs vs. 16-19 yrs), gender groups (male vs. female), racial groups (White, African American, Asian/American Indian/Pacific Islander, and multi-racial), ethnic groups (Hispanic vs. non-Hispanic), adolescents with differential baseline motivation status (highly motivated adolescents vs. less motivated), and adolescents with differential self-efficacy (high vs. low) (PCORI Methodology Standard HT-2). We recognize the possibility that additional subgroups may

arise in the course of the analyses described above as we identify which factors modify the associations. (PCORI Methodology Standard HT-4) Our stepped wedge design allows us to employ both within participants and between participants information to estimate and compare treatment effects.

As we have outlined in the Statistical Analysis section, the primary analysis will be based on mixed-effects regression models in the following form, for example, when examining PCP outcomes (similar models will be applied to adolescent outcomes):

$$Y_{ijk} = \mu + \alpha X_{ijk} + \beta_k T_k + b_i + b_{ij} + \gamma \text{covariates} + \epsilon_{ijk},$$

in which Y_{ijk} denotes the appropriate preventive counseling rate for j th PCP within i th clinic at time interval k , X_{ijk} is a binary indicator of exposure to the intervention (predictor of interest), T_k is a binary indicator of the k th assessment time interval, b_i and b_{ij} are clinic and PCP specific random effects that account for the within clinic and within PCP correlations, ϵ_{ijk} is the error term. Adjustment for additional clinic-level or PCP-level confounding variables can be incorporated into the model as well. With this model, the fixed effect α captures the treatment effect, while fixed effects β_k 's aim to capture any temporal trend. Using this approach, both within-PCP and between PCP information will be used to estimate the treatment effect.

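### Tests of effect modification by motivation and self-efficacy use high/low groups with no stated cut-point, which costs precision; self-efficacy is also not tied to baseline, and its survey schedule is inconsistent

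*Combined protocol and SAP*

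**What the plan says.** Section 3.3.3 of the combined protocol and SAP lists the characteristics across which the effect may vary. Two come from questionnaire scores: "adolescents with differential baseline motivation status (highly motivated adolescents vs. less motivated" and "adolescents with differential self-efficacy (high vs. low". The first is tied to baseline and the second has no time point. Neither has a cut-point. The analysis then has two steps: the regression model is fitted in each subgroup and the effects are inspected, after which a treatment-by-group term is added and its coefficient, α₃, is tested with a Wald test. No model with the uncut score is described.

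Table 1 in Section 3.2 places "Health Self-Efficacy" under its moderators heading, with time points "T1(A), T2 (A), T3(A), T4(A), T5(A". Section 3.1 describes the surveys differently:

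- **T1:** the items include "interest in discussing health risks with the PCP, and self-efficacy".
- **T2 (one day):** adolescents are asked to "complete a survey about their motivation for health, perception of PCP communication, and experiences". Self-efficacy is not named.
- **T3 to T5 (3, 6 and 12 months):** earlier assessments are repeated "except the questionnaires related to delivery of preventive counseling, demographics, interest in discussing health risks with PCP, and self-efficacy".

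**The concern.** There are two separate issues.

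First, cutting a score in two before testing an interaction treats everyone on the same side of the cut as alike. If the effect changes steadily with the score, that discards information. Interaction tests are already imprecise. Here there are about 300 adolescents clustered within about 30 providers, and Section 3.3.3 itself foresees a large number of subgroup analyses. An unstated cut-point also leaves a choice that could be made after the data are seen.

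Second, a modifier should be fixed before exposure. Under Section 3.1, intervention adolescents receive motivational feedback after completing the T1 screening survey, and the visit with the trained provider follows. Self-efficacy at T2 or later could therefore be changed by the intervention. Subgroups formed on such a value remove the part of the effect that runs through self-efficacy, and the two periods are no longer comparable within a subgroup.

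**Working it through.** The plan states no power, effect size or information figure for the heterogeneity analysis, so there is no figure to reproduce.

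**1. Cost of the high/low split**

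Inputs from the documents: about 300 adolescents (Section 2.1) and retention above 85% (Section 3.3.1), so 0.85 × 300 = 255. Assumptions: linear interaction, two-sided α of 0.05, 80% power with the uncut score, no clustering.

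The share of information kept is the squared correlation between the score and its high/low indicator. With a proportion p on one side of the cut:

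- normal score: kept = φ(c)² / [p(1 − p)], where c is the cut in SD units;
- uniform score: kept = 3p(1 − p).

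At the median of a normal score: 0.3989² / 0.25 = 2/π = 0.637, so 36.3% is lost. The standard error relative to the effect rises by √(1/0.637) = 1.25. In effective size, 300 × 0.637 ≈ 191 and 255 × 0.637 ≈ 162.

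Power after the cut is Φ[(1.960 + 0.842) × √0.637 − 1.960] = Φ(0.275) = 0.61. A simulation of 6,000 trials of 300 (150 per condition, no clustering) gave 79.7% with the continuous score and 58.8% with the median split.

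| Score | Split | Information lost | Power, from 80% |
|---|---|---|---|
| Uniform | 50/50 | 25% | 68% |
| Normal | 50/50 | 36% | 61% |
| Uniform | 30/70 | 37% | 60% |
| Normal | 40/60 | 38% | 60% |
| Normal | 30/70 | 42% | 57% |
| Normal | 20/80 | 51% | 50% |

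More lopsided cuts cost more: a normal score cut 10/90 loses 66%.

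**2. The self-efficacy schedule**

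| Time | Table 1 | Section 3.1 | Conflict |
|---|---|---|---|
| T1 | listed | listed | none |
| T2 | listed | not named | omission only |
| T3 to T5 | listed | expressly left out | contradiction |

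**3. If post-visit self-efficacy defined the groups**

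This is an illustration with assumed inputs. The intervention raises T2 self-efficacy (SD 1) by 0.3. Self-efficacy acts on the outcome with coefficient m = 0.3 or 0.5. The direct effect is 0.2. The total effect is 0.2 + 0.3m, that is 0.29 or 0.35, in outcome units with residual SD 1.

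Splitting at the T2 median removes about (2/π) × 0.3 × b from the effect in each group, where b is the slope of the outcome on T2 self-efficacy at a given exposure.

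- **No unmeasured common cause (b = m):** 0.29 − 0.637 × 0.3 × 0.3 = 0.233 (20% too small); 0.35 − 0.637 × 0.3 × 0.5 = 0.254 (27% too small).
- **With an unmeasured common cause** acting on self-efficacy (0.6) and on the outcome (0.4), b = m + 0.24: 0.29 − 0.637 × 0.3 × 0.54 = 0.187 (36% too small); 0.35 − 0.637 × 0.3 × 0.74 = 0.209 (40% too small).

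Simulation agrees to within about 0.002. Groups formed on T1 self-efficacy recovered the total effect in every case.

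**The case against.** The strongest reply on timing is that the plan treats self-efficacy as a baseline characteristic. Section 3.1 collects it at T1 with age, gender and race/ethnicity, and drops it later together with demographics. The other modifiers in Section 3.3.3 are background traits or are expressly baseline. If Section 3.1 governs, no T3 to T5 values will exist. This stands. A reader might infer that post-visit subgroups are intended, but no passage says so; the text only leaves them open.

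Nor does silence about T2 in Section 3.1 show exclusion. That description is a summary, and it also omits the number of visits with the provider, which Table 1 schedules at T2. The contradiction is express at T3 to T5 only.

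A reader might also infer from the attenuation figures that the formal test or the main result is biased. The illustration does not show that. It contains no true interaction, and the high and low T2 groups gave nearly equal effects, so their difference, which α₃ tests, stayed near zero. What shrinks is the effect displayed within each subgroup in the first step.

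On splitting, groups do not require a linear interaction, and they serve the stated goal of finding who benefits most. That is a fair reason to keep a grouped display, but not to base the formal test on it.

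Finally, Section 3.3.2 requires an analysis plan to be presented to the study team and the advisory board before each question is analysed, so time point and cut-point could still be set there. That lowers the urgency, but the present text describes only a grouped test.

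**Conclusion.** The point holds for a secondary analysis, at low to moderate priority.

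The firmest part is the split. Section 3.3.3 bases its formal test on two-level versions of motivation and self-efficacy with no cut-point. The loss is about 36% of the information for a normal score cut at the median with a linear interaction, and about 25% to 51% over the cases tabulated. It would be tempting to report a loss of a third as a property of this trial. The documents do not support that, because they give no scale range, distribution or cut-point for either measure.

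The schedule conflict at T3 to T5 is real and affects what is collected. The missing time point for self-efficacy leaves open a subgroup definition that could make displayed subgroup effects about 20% to 40% too small. Those figures rest wholly on assumed inputs, and the upper end needs an unmeasured common cause.

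**What to change.** In Section 3.3.3:

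- Define both modifiers as T1 scores.
- Base the formal interaction test on the centred continuous score in place of the group indicator.
- Show the estimated effect at, for example, the 25th and 75th percentiles. If high/low groups are also shown, set the cut-point in advance and label them as display only.
- State that no T2 to T5 value will be used as a modifier.

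In Table 1 and Section 3.1, reconcile the self-efficacy row with the survey descriptions, including whether the item is asked at T2.

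The change is a few sentences and one table row, and it uses data already planned at T1. If the later self-efficacy items are dropped, the surveys become shorter. The one statistical cost is that a linear form is assumed; a flexible term or the grouped display can check it.

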intervention effects. Data set documentation will then be developed and distributed to the study team. Before carrying out analyses addressing each of the research questions, an analysis plan will be formally presented to the study team and Project Advisory Board so a wide range of expertise and experience is brought to bear on each work product of the team.

Some key features of the stepped wedge design require special consideration in the planned analyses. First, the design involves unidirectional cross-over from the control arm to the intervention arm for all PCPs. This has to be captured by an indicator specific to PCP and time point. Second, there are natural hierarchical structures in the data with PCPs nested within clinics, patients nested within PCPs, and repeated assessments made within patients for some outcomes, such as health risk behaviors. Because different patient samples will be surveyed at each time point, within patient correlation over time should not be strong. Still, clustering at the clinic and PCP-levels needs to be examined in all analyses. Third, secular time trends need to be carefully examined and separated from the intervention effect. Based on these considerations, we will focus on model-based approaches (linear or generalized linear mixed effects models) for the main analyses, in addition to standard hypothesis testing techniques.

Aim 1 will compare intermediary targets at all clinics before and after the intervention using an analytic approach that both accounts for design features, repeated assessments within adolescents, time trends in these target behaviors during study period and adjust for potential confounders. For this aim we will use patients as the units of analysis. We will consider outcomes at the level of the patient (adolescent reported motivation for health and provision of appropriate preventive counseling).

Our primary analysis will be based on a set of mixed effects regression models. As an illustration, let's consider the adolescent self-reported health motivation (readiness to change, as other adolescent reported outcomes can be modelled in a similar fashion. Specifically, we will consider the following regression model:

$$Y_{ijk} = \mu + \alpha X_{ijk} + \beta_k T_k + \gamma_k X_{ijk} * T_k + b_i + b_{ij} + \varphi \text{Covariates} + \varepsilon_{ijk},$$

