in which Y_{ijk} denotes the health motivation reported by j th patient within i th provider at k th time interval, X_{ijk} is a binary indicator of exposure to the intervention for the provider and the predictor of interest, T_k is a binary indicator of the k th assessment, b_i and b_{ij} are PCP and adolescent specific random effects that account for the within PCP and within adolescent correlations, and ε_{ijk} is the error term. Additional patient-level or PCP-level confounding variables can be adjusted in the model as well.

With this model, the fixed effects α captures the treatment effects on mean responses and time-by-intervention interaction coefficients γ_k 's captures the treatment effects across time. Fixed effects β_k 's aim to capture any temporal trend or learning effects. Using this approach, both within-adolescents and between adolescents information will be used to estimate the treatment effects. All coefficients will be tested using Wald test. Also note this

model framework is flexible enough that a patient can be enrolled at any time during the study and the model can accommodate different numbers of post-intervention assessments. For example, for an adolescent enrolled after his/her PCP has received intervention, all X_{ijk} 's would take value 1 for that subject.

We will apply linear mixed effects models for Gaussian outcome Y_{ijk} , and generalized linear mixed effects models for other types of outcomes (e.g., logistic model for binary outcome).

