For *Aim 2*, analyses will be based on patient survey responses to the 8-item satisfaction scale, patient perception of PCP communication, and the summary health risk variable, which will all be treated as continuous response variables. The summary health risk variable constructed from a count of dichotomized key risk behaviors (as shown in Table 2). First, satisfaction levels and risk behaviors will be summarized for each period (pre- and post-intervention) and will be compared using two sample t-tests. For the main analysis, we will apply mixed effects models similar to those proposed in Aim 1 to examine the intervention effect. For patient satisfaction, PCP satisfaction, adolescent's perception of PCP communication and health risk behaviors, the analysis will be cross-sectional comparisons at one day following the primary care visit. Let Y_{ij} denotes the satisfaction at one-day post visit of adolescent j within PCP i , let X_{ij} denote whether the PCP has received intervention at the time of visit, then the following mixed effects model can be applied

$$Y_{ij} = \mu + \alpha X_{ij} + b_i + \varphi \text{Covariates} + \varepsilon_{ij},$$

where b_i accounts for within-PCP correlations for adolescents seen by the same PCP. The fixed effect α captures the intervention effect on the patient satisfaction. Similar model can be applied to PCP outcomes and we can account for within-clinic correlations as well.

When examining the intervention effects on adolescents individual risky behaviors (alcohol use, marijuana use, unprotected sexual activity, depression, physical activity, healthy food consumption, seatbelt and helmet use) at baseline, 3, 6, and 12 months after the primary care visit, same modeling framework as outlined for Aim 1 can be applied.

3.3.3 Heterogeneity of Treatment Effects.

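### The primary model has no clinic-by-interval or clinic-varying effect, so the standard error for the intervention effect will be too small if clinics drift differently or respond differently

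*Combined protocol and SAP*

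**What the plan says.** Section 3.1 describes a stepped wedge in six clinics, with the intervention "rolled-out sequentially to the clinics, chosen in random order, over spaced time intervals". Section 3.3.3 says "the primary analysis will be based on mixed-effects regression models in the following form" and writes an intervention indicator X with coefficient α, fixed effects β_k for each time interval, two random intercepts, covariates and a residual. The intercepts are "clinic and PCP specific random effects that account for the within clinic and within PCP correlations". The outcome in that equation "denotes the appropriate preventive counseling rate for" a PCP in a clinic at an interval, and similar models are promised for adolescent outcomes. The β_k "aim to capture any temporal trend. Using this approach, both within-PCP and between PCP information will be used to estimate the treatment effect"; they carry no clinic index.

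The models in section 3.3.2 hold less. The Aim 1 model has "PCP and adolescent specific random effects that account for the within PCP and within adolescent correlations" and no clinic term, and its T_k is defined as an indicator of the assessment. The Aim 2 model for one-day outcomes has a PCP intercept and no time term; of PCP outcomes the text adds that "we can account for within-clinic correlations as well". Coefficients in the Aim 1 model are tested by Wald test. On dependence in general, section 3.3.2 says that "clustering at the clinic and PCP-levels needs to be examined in all analyses" and that secular trends must be separated from the intervention effect.

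**The concern.** Clinic and PCP intercepts with common interval effects make two assumptions. First, two adolescents from one clinic are equally alike whether they were seen in the same interval or many months apart. Second, the intervention moves every clinic by the same amount. In a stepped wedge, much of the information on α comes from changes within a clinic from one interval to the next. Change that is particular to a clinic, such as staffing, local events or a shift in case mix, is therefore the relevant error for that comparison, and the model has no term for it.

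The shared shock then goes into the residual. In the literal section 3.3.3 equation it becomes PCP-by-interval noise, taken as independent across PCPs of one clinic. For adolescent outcomes it becomes patient noise. Either way the model counts more independent information than there is, and its intervals for α are too short.

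The plan itself makes such variation plausible. Training and three feedback reports go to PCPs, follow-up data are returned to providers by clinic, recruitment is rolling and organized by clinic, and different patients are surveyed at each time point.

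**Working it through.** **Inputs from the documents.** 6 clinics; about 30 PCPs (6 × 5); about 300 adolescents (1000 × 0.30), or 50 per clinic if spread evenly. There is no power calculation to reproduce: sample size calculations are mentioned but not shown, and no ICC, SD, effect size or correlation over time is stated. The figure with the step timetable is not available here.

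**Assumptions.** Gaussian outcome, one assessment per adolescent, total variance 1, PCP variance 0.02. ICC is the within-interval clinic correlation, from 0.01 to 0.10. r is the ratio of between-interval to within-interval clinic correlation, from 0.5 to 1.0 (r = 1 means no drift). There are six steps of one clinic (7 intervals) or three steps of two clinics (4 intervals).

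Variance components:
- clinic: ICC × r
- clinic-by-interval: σ²_ct = ICC × (1 − r)
- residual: σ²_e = 1 − ICC − 0.02

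**Step 1: hand approximation.** Let n be the adolescents per clinic-interval. The mean of such a cell has true variance, beyond the intercepts, of σ²_ct + σ²_e/n. A model without the term takes it as (σ²_ct + σ²_e)/n. The ratio of true to reported SE is then roughly √(1 + (n − 1)ρ), with ρ = σ²_ct/(σ²_ct + σ²_e).

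For ICC 0.10 and r = 0.5: σ²_ct = 0.05, σ²_e = 0.88, ρ = 0.05/0.93 = 0.0538.
- Six steps: n = 50/7 = 7.14, so √(1 + 6.14 × 0.0538) = 1.15.
- Three steps: n = 50/4 = 12.5, so √(1 + 11.5 × 0.0538) = 1.27.

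**Step 2: analytic calculation.** The large-sample REML limit of the model with clinic and PCP intercepts only gives the reported SE of α. The sandwich formula under the true covariance gives the true SE. This isolates the omitted term, because no small-sample effect enters. Coverage is 2Φ(1.96/ratio) − 1.

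| Steps | ICC | r | Reported SE | True SE | Ratio | Hand ratio | Coverage of 95% interval |
|---|---|---|---|---|---|---|---|
| 6 | 0.05 | 1.0 | 0.182 | 0.182 | 1.00 | 1.00 | 95.0% |
| 6 | 0.01 | 0.8 | 0.169 | 0.169 | 1.004 | 1.006 | 94.9% |
| 6 | 0.05 | 0.8 | 0.181 | 0.186 | 1.03 | 1.03 | 94.4% |
| 6 | 0.05 | 0.5 | 0.178 | 0.189 | 1.06 | 1.08 | 93.5% |
| 6 | 0.10 | 0.8 | 0.184 | 0.195 | 1.06 | 1.07 | 93.5% |
| 6 | 0.10 | 0.5 | 0.182 | 0.207 | 1.14 | 1.15 | 91.6% |
| 3 | 0.05 | 0.8 | 0.196 | 0.206 | 1.05 | 1.06 | 93.8% |
| 3 | 0.05 | 0.5 | 0.194 | 0.218 | 1.12 | 1.14 | 92.0% |
| 3 | 0.10 | 0.5 | 0.197 | 0.247 | 1.25 | 1.27 | 88.2% |

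With no drift but an intervention effect that varies by clinic (variance 0.04, SD 0.2; six steps, ICC 0.05), the ratio is 1.09. With r = 0.8 as well, it is 1.12.

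**Step 3: the literal section 3.3.3 equation.** With PCP-by-interval rates as the outcome, the six-step ratios are 1.03 (ICC 0.05, r 0.8), 1.06 (0.05, 0.5) and 1.13 (0.10, 0.5). With three steps at 0.10 and 0.5 the ratio is 1.21.

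**Step 4: simulated coverage.** 1000 trials per setting, Wald z interval, Monte Carlo error just under 1 percentage point:

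| Steps, ICC, r | Without the term | With the term |
|---|---|---|
| 6, 0.05, 0.8 | 93.1% | 94.3% |
| 6, 0.05, 0.5 | 90.6% | 91.9% |
| 6, 0.10, 0.5 | 89.3% | 92.5% |
| 3, 0.10, 0.5 | 85.6% | 91.7% |

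With no drift at all, the planned model covers 92.4% (six steps) or 93.2% (three steps). Part of every shortfall in this table therefore comes from using a z interval with six clinics.

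**Step 5: cross-check.** A separate simulation used a clinic intercept only, 7 intervals, 7 adolescents per cell and 1200 replicates. Empirical SD over mean SE was 0.186/0.177 = 1.05 with no drift. For (0.05, 0.8), (0.05, 0.5) and (0.10, 0.5) it was 0.192/0.176 = 1.09, 0.194/0.172 = 1.13 and 0.213/0.178 = 1.20. Dividing each by the no-drift value leaves 1.04, 1.07 and 1.14, in line with step 2.

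**The case against.** Four arguments can be made for the plan as written.

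- **The harm is conditional.** A reader might infer that the intervals are too narrow for every outcome. The documents do not support that. With no clinic-by-interval variance and a common effect, the ratio is exactly 1; at ICC 0.01 it is 1.004. No variance component is stated, so every non-zero figure above rests on assumed inputs. This stands.
- **Small-sample error is easily mixed in.** A reader might take the whole gap between 85.6% or 89.3% and 95% as the price of the missing term. It is not, because the no-drift model already falls short with six clinics. Nor does adding the term restore 95%. This stands, and it is why the size is quoted from the analytic ratios.
- **The section 3.3.3 equation is an example for PCP outcomes.** The term cannot simply be added to the section 3.3.2 models, which lack a clinic intercept or calendar time. This stands and shapes the fix. Binary outcomes, for which section 3.3.2 plans logistic mixed models, were not simulated.
- **Section 3.3.2 already calls for clustering and secular trends to be examined, and for an analysis plan to be presented before analysis.** This does not answer the point. Examining is not a specified structure, and the only time effects written are common to all clinics. The interactions in sections 3.3.2 and 3.3.3 are fixed effects for assessment time and patient subgroup, and do not represent clinic variation.

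**Conclusion.** The structural point holds: even the most complete model in the plan omits clinic-specific change over time and clinic-specific response, and no robust variance or permutation test makes up for it. In every setting examined with either source of variation, the reported SE of α was below the true SE.

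The size is unknown from the documents. For drift under the assumptions listed, the true SE is about 0 to 14% above the reported SE with six steps and up to about 25% above with three. A clinic-varying effect with SD 0.2 alone adds about 9% with six steps. At an ICC of 0.01 the matter is negligible. The documents support a cheap improvement to prespecification, not a finding that the planned intervals are wrong for all outcomes.

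**What to change.** 1. For adolescent and PCP outcomes, prespecify a random clinic-by-calendar-interval effect alongside the clinic and PCP intercepts. Keep it in the model whatever its p-value.
2. In the Aim 1 and Aim 2 models of section 3.3.2, first add the clinic intercept and fixed calendar-interval effects. In Aim 1, T_k indexes assessments since the visit and does not stand in for calendar time; the Aim 2 one-day model has no time term.
3. Report, as a sensitivity analysis, a model that also lets the effect of X vary by clinic.

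The cost is one further variance term, and in section 3.3.2 the clinic intercept and interval effects that the term presupposes; no extra participants are needed. Intervals become slightly wider. For some outcomes the variance may be estimated at or near zero, in which case the result equals that of the model without the term. Fixing the structure before outcome data are seen avoids a later choice between narrower and wider intervals. The term does not by itself give nominal coverage with six clinics; a small-sample correction or permutation test has to be settled separately.
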